3.2 Exclusion Criteria

Patients meeting any of the following exclusion criteria will not be able to participate in this study:

3.2.1 Is currently participating in or has participated in a study of an investigational agent or using an investigational device within 4 weeks of the first dose of treatment.

3.2.2 Has a diagnosis of immunodeficiency or is receiving systemic steroid therapy or any other form of immunosuppressive therapy within 7 days prior to the first dose

of HiDAC treatment. **NOTE:** use of steroid eye drops starting at the time of HiDAC administration is allowed.

[figure not shown]
- 3.2.3** Has a known history of active TB (Bacillus Tuberculosis)
- 3.2.4** Hypersensitivity to pembrolizumab or any of its excipients
- 3.2.5** Has had a prior monoclonal antibody within 4 weeks prior to study Day 1 or who has not recovered (i.e., \leq Grade 1 or at baseline) from adverse events due to agents administered more than 4 weeks earlier.
- 3.2.6** Has had prior chemotherapy, targeted small molecule therapy, or radiation therapy within 2 weeks prior to study Day 1 or who has not recovered (i.e., \leq Grade 1 or at baseline) from adverse events due to a previously administered agent.
- Note: Subjects with \leq Grade 2 neuropathy are an exception to this criterion and may qualify for the study.
 - Note: If subject received major surgery, they must have recovered adequately from the toxicity and/or complications from the intervention prior to starting therapy.
- 3.2.7** Has a known additional malignancy that is progressing or requires active treatment. Exceptions include basal cell carcinoma of the skin, squamous cell carcinoma of the skin that has undergone potentially curative therapy, or in situ cervical cancer that has undergone potentially curative therapy.
- 3.2.8** Has known active central nervous system (CNS) leukemia; subjects with previously treated CNS disease may participate provided they are stable (without evidence of active disease by imaging for at least 4 weeks prior to the first dose of treatment, and any neurologic symptoms have returned to baseline), have no evidence of new or enlarging brain metastases, and are not using steroids for at least 7 days prior to D1 of treatment.
- 3.2.9** Has active autoimmune disease that has required systemic treatment in the past 2 years (i.e. with use of disease modifying agents, corticosteroids or immunosuppressive drugs). Replacement therapy (eg., thyroxine, insulin, or physiologic corticosteroid replacement therapy for adrenal or pituitary insufficiency, etc.) is not considered a form of systemic treatment.
- 3.2.10** Has evidence of interstitial lung disease or a history of (non-infectious) pneumonitis that required steroids or current pneumonitis.
- 3.2.11** Has a history or current evidence of any condition, therapy, or laboratory abnormality that might confound the results of the trial, interfere with the

subject's participation for the full duration of the trial, or is not in the best interest of the subject to participate, in the opinion of the treating investigator.

- 3.2.12 Has known psychiatric or substance abuse disorders that would interfere with cooperation with the requirements of the trial
- 3.2.13 Is pregnant or breastfeeding, or expecting to conceive or father children within the projected duration of the trial, starting with the pre-screening or screening visit through 120 days after the last dose of trial treatment
- 3.2.14 Has received prior therapy with an anti-PD-1, anti-PD-L1, anti-PD-L2, anti-CD137, or anti-Cytotoxic T-lymphocyte-associated antigen-4 (CTLA-4) antibody (including ipilimumab or any other antibody or drug specifically targeting T-cell co-stimulation or checkpoint pathways)
- 3.2.15 Has a known history of Human Immunodeficiency Virus (HIV) (HIV 1/2 antibodies).
- 3.2.16 Has known active Hepatitis B (e.g., HBsAg reactive) or Hepatitis C (e.g., HCV RNA qualitative is detected).
- 3.2.17 Has received a live vaccine within 30 days prior to the first dose of trial treatment
Note: Seasonal influenza vaccines for injection are generally inactivated flu vaccines and are allowed; however intranasal influenza vaccines (e.g., Flu-Mist®) are live attenuated vaccines, and are not allowed.
- 3.2.18 Has uncontrolled intercurrent illness including, but not limited to, active and uncontrolled infection, symptomatic congestive heart failure, unstable angina pectoris, and uncontrolled symptomatic cardiac arrhythmia. Patients with infection under active treatment and controlled with antibiotics are eligible.
- 3.2.19 Diagnosed with acute promyelocytic leukemia (APL, M3)
- 3.2.20 Receipt of previous allogeneic stem cell transplant; receipt of previous autologous transplant for AML or non-AML condition is allowed

4.0 TREATMENT PLAN

4.1 Schema

¹During Maintenance, bone marrow biopsy to be done after every 4th cycle of pembrolizumab for year 1, and every 8th cycle of pembrolizumab during years 1-2.

²See Time and Events Table for schedule of serial blood samples for correlative research

This is a phase 2, open-label, multicenter, single-arm study evaluating HiDAC salvage induction chemotherapy followed by pembrolizumab in the relapsed/refractory AML setting. Toxicity will be assessed during treatment via NCI CTCAE v4.0. Tumor specimens from a pre-study bone marrow biopsy and post-treatment bone marrow biopsies as well as serial blood samples will be collected for correlative studies.

Pembrolizumab 200 mg is administered IV once as monotherapy, 14 days after the initiation of HiDAC salvage induction chemotherapy. Patients who have a response (i.e., PR/CR/CRi) to induction phase will receive maintenance pembrolizumab at 200 mg IV every 3 weeks for up to 2-years of maintenance therapy (i.e., beginning on day 1 of maintenance).

4.2 Induction Phase

Treatment will be administered as an inpatient. Patients will be discharged from the inpatient unit after receiving pembrolizumab per institutional standards. All patients will receive standard high dose cytarabine (HiDAC) for salvage induction therapy dose-adjusted for age. Patients <60 years will receive HiDAC 2 gm/m² IV Q12hours days 1-5 while patients ≥60 years will receive HiDAC 1.5 gm/m² IV Q12hours days 1-5. Pembrolizumab will be administered as a fixed dose of 200 mg IV on day 14. Prior to pembrolizumab administration, patients must continue to meet eligibility for laboratory parameters as outlined in section 3.1. If

laboratory abnormalities exist on day 14, (or any patient with uncontrolled intercurrent illness or other abnormalities deemed by the PI to be unsafe to administer pembrolizumab), pembrolizumab administration can be delayed for 1 week, up to day 21, provided laboratory abnormalities correct themselves to levels defined in section 3.1 with supportive care. Patients who are ineligible for pembrolizumab administration by day 21 will be removed from the study and replaced by another subject. A disease assessment with a bone marrow biopsy will occur after patients have achieved full hematologic recovery as per standard of care, defined as absolute neutrophil count $\geq 1,000/\text{mcL}$ and platelet count $\geq 100,000/\text{mcL}$. If full hematologic recovery does not occur by day 45 +/- 2 days, a bone marrow biopsy will take place regardless. Patients without evidence of active leukemia on disease assessment but without full hematologic recovery by day 45 +/- 2 days will require a repeat bone marrow biopsy upon full hematologic recovery. Patients who achieve a CRi, will be followed with serial blood counts (weekly) for up to 30 days after bone marrow biopsy post-induction is performed. Those who achieve subsequent full hematologic recovery (within 30 days of CRi) will require an additional bone marrow biopsy to document full CR status. If they do not achieve full hematologic recovery within 30 days, they will remain designated as a CRi. Patients who have achieved a PR, CR or CRi will receive maintenance pembrolizumab (see section 4.3). Please see section 6.9 for response definitions.

REGIMEN DESCRIPTION				
Agent	Premedications; Precautions	Dose	Route	Schedule
Cytarabine	Dexamethasone 0.1% ophthalmic eye drops 1 hour before cytarabine and Q6 hours both eyes days 1-12. See section 4.4.5 for prevention of tumor lysis syndrome	2 gm/m ² Q12hours (1.5 gm/m ² in ≥ 60 years)	IV over approximately 2 hours, per institutional guidelines	Days 1-5
Pembrolizumab	None	200 mg	IV over 30 minutes	Day 14

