1.0 BACKGROUND AND RATIONALE

1.1 Study Synopsis

This is an open-label, single arm, multicenter phase 2 study of standard salvage high dose cytarabine (HiDAC) on days 1 through 5 followed by a single dose of the humanized monoclonal antibody targeted against cell surface receptor programmed cell death-1 (PD-1), pembrolizumab, on day 14 as induction therapy in patients with relapsed and refractory acute myeloid leukemia (AML). Patients who achieve at least a partial response (PR) post-induction will continue on pembrolizumab every 3 weeks for up to 1 year of maintenance therapy. We plan to enroll 37 patients in a Simon's two-stage design.

The hypothesis of this study is that HiDAC followed by pembrolizumab will be effective in relapsed and refractory AML with a combined complete remission (CR)/CR with incomplete recovery (CRi) rate of $\geq 40\%$, superior to a historical control of 20%. We also hypothesize that the rate of unacceptable toxicity associated with HiDAC followed by pembrolizumab will not significantly exceed 20% (see section 2.4.2). Secondary endpoints include toxicity of this combination when used as induction, overall objective response rate (CR+CRi +PR) post-induction, toxicity of pembrolizumab maintenance in those patients with a response after induction, and progression-free survival (PFS), relapse-free survival (RFS) and overall survival (OS) in patients who receive maintenance pembrolizumab. We will also explore for an association between potential immune biomarkers and clinical outcomes with pembrolizumab. The overarching goals of these correlative studies are: 1) to identify and characterize mechanisms involved in T cell dysfunction in AML, 2) to identify potential predictive biomarker candidates to allow better selection of AML patients who may benefit from pembrolizumab, and 3) to identify new pathways that could be targeted to enhance the efficacy of pembrolizumab in AML.

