Recent studies have suggested that cytarabine alone has response rates 15-20% in relapsed and refractory AML patients. A randomized phase III study compared vosaroxin + cytarabine versus cytarabine alone (1 gm/m² IV daily for 5 days) in relapsed and refractory AML patients. The CR rate for patients on the vosaroxin + cytarabine arm was 30% versus 16% in patients on the cytarabine only arm.⁹ An international randomized phase III study of elacytarabine compared with physician's choice, which included high dose cytarabine, also showed CR rates of approximately 20% in the physician's choice arm.¹⁰ Additionally, a randomized phase II study by ECOG recently compared three different promising regimens for relapsed and refractory AML: Arm A: carboplatin + topotecan, Arm B: flavopiridol + cytarabine + mitoxantrone (FLAM), Arm C: Sirolimus + Mitoxantrone + Etoposide + Cytarabine. FLAM was shown to be the most effective regimen in this trial, with a CR rate of 28%, while Arm A and Arm C produced CR rates of 14% and 15%, respectively.¹¹

It is unclear whether 3 gm/m² of cytarabine is necessary and whether this dose is superior to 2 gm/m². Moreover, high doses of cytarabine (>2 gm/m²) appear to increase the risk for cerebellar toxicity, especially in older patients and those with renal disease.¹² HiDAC at doses of 1-2 gm/m² has also been evaluated in combination with other chemotherapy agents in relapsed and refractory AML patients, such as topoisomerase inhibitors (mitoxantrone and etoposide),^{3,13-15} fludarabine¹⁶, cladribine^{17,18}, and clofarabine.^{19,20} Response rates seen with these combinations range from 20-50% (median duration of response <9 months), with significant toxicities; 30-day mortality rates of these regimens range from 10-30%.

Given these data, there is a high unmet need to develop safe and effective novel therapeutic regimens for patients with refractory and relapsed AML. Investigational therapies are warranted in relapsed and refractory AML and are highly recommended over other conventional chemotherapy regimens.^{21,22}

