6.9 Assessment of Efficacy

Patients who have received pembrolizumab within the induction phase (cycle) will be evaluable for assessment of response and progression. Efficacy of treatment will be assessed by a bone marrow biopsy at the time of hematologic recovery (i.e., absolute neutrophil count $\geq 1,000/\text{mcL}$ and platelet count

$\geq 100,000/\text{mcL}$), or by day 45 +/- 2 days of induction treatment, whichever occurs first. Response will be assessed by standard international criteria proposed by the European LeukemiaNet Guidelines in AML.²¹

Complete remission (CR): Bone marrow blasts $< 5\%$; absence of Auer rods; absence of extramedullary disease; absolute neutrophil count $\geq 1,000/\text{mcL}$; platelet count $\geq 100,000/\text{mcL}$; independence of red cell transfusions

Complete remission with incomplete recovery (CRi): All CR criteria except for residual neutropenia ($\leq 1,000/\text{mcL}$) or thrombocytopenia ($\leq 100,000/\text{mcL}$) plus independent of platelet transfusions.

Partial response (PR): bone marrow blasts 5-25% and decrease of pretreatment bone marrow blast % by $\geq 50\%$; all hematologic criteria of CR.

Patients who achieve a PR to induction phase and then achieve CR after maintenance pembrolizumab will be assessed as an overall CR to study treatment.

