8.0 STATISTICAL CONSIDERATIONS

8.1 Study Design and Sample Size

This is a multi-center prospective open-label single arm phase 2 study assessing the activity of age-adjusted HiDAC (<60 years: 2 gm/m² IV Q12hours days 1-5; ≥60 years: 1.5 gm/m² IV Q12hours days 1-5) salvage induction treatment followed by pembrolizumab 200 mg IV on day 14 for relapsed or refractory AML patients.

The subjects who achieve a response (CR, CRi, or PR) to induction phase HiDAC followed by pembrolizumab 200 mg IV on day 14, as assessed by standard international European LeukemiaNet Guidelines in AML,²¹ will receive pembrolizumab 200 mg IV Q3weeks of maintenance therapy beginning 10-30 days following full hematologic recovery from induction phase. Maintenance treatment will continue until disease progression, toxicity, physician and/or patient discretion, or up to 1 year of treatment.

Simon's like two-stage design with relaxed stopping for futility will be used.⁵³ The null hypothesis that the true CR rate (CR/CRi) for HiDAC followed by pembrolizumab is 20% will be tested against a one-sided alternative hypothesis. In this study, "relaxed stopping" refers to inclusion of PR in the first stage as some of these PRs may convert to a CR during maintenance. In the first stage, 19 patients will be enrolled. If the number of patients who achieve a CR/CRi plus the number of patients with PR is equal to 4 or fewer in these 19 patients, the study will be stopped. Otherwise, 18 additional patients will be enrolled for a total of 37 patients. The null hypothesis will be rejected if 12 or more CR/CRi's are observed in 37 patients.. Assuming that the PR rate has a uniform distribution, Uniform (0, 0.05), under H₀, this design yields a type 1 error rate of at most 5% and power of at least 84% when the true CR rate for HiDAC followed by pembrolizumab is 0.4.

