8.3 Data Analysis Plans

The primary endpoint of this study is the overall CR rate (CR+CRi) after HiDAC salvage followed by pembrolizumab on day 14. Responses will be assessed by standard international European LeukemiaNet Guidelines.²¹

Secondary endpoints include the following:

- Rates of unacceptable toxicity defined as any drug-related grade 3 non-hematologic toxicity (exceptions: fever, rash, infection, infusion reactions, nausea, fatigue and anorexia) lasting for >7days despite supportive care, or any drug-related grade ≥ 4 non-hematologic toxicity (excluding infection)
- Clinician assessed toxicity of HiDAC followed by pembrolizumab will be classified and graded according to NCI CTCAE, version 4.0.
- Objective overall response rates will be defined as PR+CR+CRi as determined by international European LeukemiaNet Guidelines in AML.²¹
- Clinician assessed toxicity of pembrolizumab maintenance will be classified and graded according to NCI CTCAE, version 4.0
- RFS will be defined as time from day 1 of CR/CRi to relapse or death from any cause.
- PFS will be defined as time from day 1 of response (i.e., PR/CR/CRi) to progression or death from any cause.
- OS will be defined as time from day 1 of treatment until date of last known follow up or death of any cause.

Survival distributions will be summarized using the method of Kaplan and Meier. We will report median time where possible. All demographic and analytic data will be summarized by descriptive statistics. Categorical data will be summarized using frequency tables while summary statistics such as means, medians, standard deviation, range, etc., will be provided for continuous data. 95% confidence intervals will be reported as well.

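### CR/CRi is counted only in patients who reach pembrolizumab, so the 5% error is not guaranteed against an all-treated 20% rate, and no CR/CRi rate in all who start cytarabine is planned

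*Combined protocol and SAP*

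**What the plan says.** - **Who is replaced.** Section 4.2, repeated in Section 4.9: "Patients who are ineligible for pembrolizumab administration by day 21 will be removed from the study and replaced by another subject".
- **Who is evaluable.** Section 6.9: "Patients who have received pembrolizumab within the induction phase (cycle) will be evaluable for assessment of response and progression".
- **The test.** Section 8.1 enrols 19 patients and stops if CR/CRi plus PR number 4 or fewer. Otherwise it continues to 37 and rejects a 20% CR/CRi rate at 12 or more. It says that "this design yields a type 1 error rate of at most 5"%, with power of at least 84% at a true rate of 40%. It does not define the denominator, mention replaced patients or assume a non-dosing rate.
- **The benchmark.** The synopsis (Section 1.1) words the hypothesis as "superior to a historical control of 20"%. Section 1.3 supplies the background: "Recent studies have suggested that cytarabine alone has response rates 15-20% in relapsed and refractory AML patients".
- **The planned analysis.** Section 8.3: "The primary endpoint of this study is the overall CR rate (CR+CRi) after HiDAC salvage followed by pembrolizumab on day 14". Neither it nor the unredacted objectives and endpoints in Section 2 include a CR/CRi rate in all patients who start cytarabine.
- **Survival is handled differently.** Objective 2.2.6 covers patients who received induction treatment, and Section 8.3 runs the clock from the start: "OS will be defined as time from day 1 of treatment until date of last known follow up or death of any cause". The synopsis, however, words OS for maintenance patients only.
- **Follow-up of undosed patients is unclear.** Sections 4.2 and 4.9 take them out of the study. Section 4.8 takes them off protocol therapy only, and Section 4.7 follows patients for up to 5 years after they leave study treatment.

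**The concern.** Selection takes place after treatment has begun. To be counted, a patient must survive to day 14–21, meet the laboratory criteria, have no uncontrolled illness (Section 4.2) and have received more than half of the planned cytarabine (Section 4.2.2). A patient who dies before dosing is not evaluable here, but would be a non-responder in an arm that counts everyone treated. The historical rates in Section 1.3 are given by trial arm with no day-14 landmark. If they are all-treated rates, the two sides of the comparison have different denominators.

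The direction of any bias depends on how undosed patients fare. If they remit less often than dosed patients, the dosed-patient rate exceeds the all-treated rate and the 5% no longer holds against an all-treated 20%. A patient barred on laboratory values might still remit, in which case there may be little or no bias. The plan as written would not report the numbers needed to tell these cases apart, so a reader could not separate selection from activity.

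**Working it through.** **1. Reproduce the stated design.** Inputs from Section 8.1: n1 = 19; continue if CR/CRi + PR ≥ 5; n = 37; reject if CR/CRi ≥ 12; PR rate q between 0 and 0.05. With p the CR/CRi rate and x the number of stage-1 CR/CRi,

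P(reject) = Σₓ Bin(x; 19, p) × P[Bin(19 − x, q/(1 − p)) ≥ 5 − x] × P[Bin(18, p) ≥ 12 − x].

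| p | q = 0 | q = 0.025 | q = 0.05 |
|---|---|---|---|
| 0.20 | 0.0471 | 0.0485 | 0.0496 |
| 0.40 | 0.841 | 0.851 | 0.858 |

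Both claims in Section 8.1 hold when the 37 are the patients counted, that is, the dosed patients. The error already sits close to 5%, so there is almost no slack.

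**2. Translate an all-treated rate into a dosed-patient rate.** Let a be the all-treated CR/CRi rate, f the fraction who start cytarabine but are never dosed, and u the CR/CRi rate among them. The dosed-patient rate is

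p = (a − f·u)/(1 − f).

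For a = 0.20, f = 0.10, u = 0: p = 0.20/0.90 = 0.2222. For a = 0.20, f = 0.10, u = 0.10: p = 0.19/0.90 = 0.2111.

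The documents give none of a, f or u for this setting, so all are assumed. The nearest figure, in Section 1.3, is for cytarabine combinations: "30-day mortality rates of these regimens range from 10-30"%. That is not attrition to day 21 on this regimen.

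**3. Probability of declaring success (q = 0.025).** The last column is the undosed fraction at which 5% is passed.

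| a | u | f = 2% | f = 5% | f = 10% | f = 20% | Passes 5% at f of about |
|---|---|---|---|---|---|---|
| 20% | 0 | 5.5% | 6.8% | 9.5% | 18.4% | 0.4% |
| 20% | 10% | 5.2% | 5.8% | 6.9% | 10.2% | 0.9% |
| 20% | 15% | 5.0% | 5.3% | 5.8% | 7.2% | 1.8% |
| 20% | 20% | 4.9% | 4.9% | 4.9% | 4.9% | never |
| 18% | 0 | 2.7% | 3.4% | 4.9% | 10.2% | 10.4% |
| 18% | 10% | 2.5% | 2.7% | 3.3% | 4.9% | 20.7% |
| 16% | 0 | 1.1% | 1.4% | 2.1% | 4.9% | 20.4% |
| 15% | 0 | 0.7% | 0.9% | 1.3% | 3.1% | 25.3% |

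For the first row, varying q over 0–0.05 gives 5.4–5.7%, 6.6–6.9%, 9.2–9.7% and 17.9–18.7%. If undosed patients remit more often than dosed ones, the error falls: a = 20%, f = 10%, u = 30% gives 3.3%.

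**4. What an all-starter rate would show.** The expected number undosed per 37 dosed is 37f/(1 − f), which is 0.8, 1.9, 4.1 and 9.3 at f = 2, 5, 10 and 20%. Take a trial that just succeeds, with undosed patients counted as non-CR:

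| Undosed | CR/CRi | Rate (exact 95% CI) |
|---|---|---|
| 0 | 12/37 | 32.4% (18.0–49.8) |
| 2 | 12/39 | 30.8% (17.0–47.6) |
| 4 | 12/41 | 29.3% (16.1–45.5) |
| 9 | 12/46 | 26.1% (14.3–41.1) |

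**The case against.** The strongest reply is that no stated figure is wrong. Section 8.1 frames the null as the rate for the two-drug regimen, and Sections 2.1, 6.9 and 8.3 use the same target. The plan never claims 5% control against an all-treated rate. That stands, and it is why the test itself should not be changed. It does not settle the comparison with an external 20%, which needs either a benchmark filtered in the same way or the numbers to judge the difference.

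The second reply is that the size is hypothetical. The 18.4% needs a true rate of exactly 20%, one starter in five undosed, and no remission among them. Section 1.3 quotes 15–20% for cytarabine alone, so 20% is the top of that range; at 16% the bound survives about 20% undosed even with no remissions among them. Section 1.3 also mostly reports CR rather than CR/CRi, which makes the benchmark less certain in either direction. All of this stands, and it limits the claim to the 5% not being guaranteed.

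Third, some of the data are already collected. Section 4.8 puts the reason for stopping on the eCRF, and Section 4.7 provides follow-up after treatment. This stands in part: nothing commits the trial to report undosed patients beside a CR/CRi rate, and the wording of Sections 4.2 and 4.9 leaves their follow-up in doubt.

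Finally, parts of the objectives and endpoints are redacted, so the missing all-starter rate is judged on the visible text. The replacement rule speaks of ineligibility, not death; that early deaths leave the denominator follows from Section 6.9.

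**Conclusion.** The concern holds. The error and power in Section 8.1 are right for patients who receive pembrolizumab. Against a 20% rate in all treated patients, the 5% is not guaranteed: it is exceeded if undosed patients remit less often than dosed ones and the benchmark really is about 20% on an all-treated basis. In the assumed scenarios at 20%, the error ranges from 4.9% (undosed patients remit at 20%) to 18.4% (20% undosed, none remitting). At 15–18% with no remissions among undosed patients, it stays within 5% until about 10–25% are undosed. The size in this trial cannot be known from the documents, and the visible analysis plan would not reveal it afterwards. This should be fixed; it does not invalidate the design.

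**What to change.** 1. **Follow-up.** Reconcile Sections 4.2 and 4.9 with Sections 4.7 and 4.8, so that undosed patients stay in follow-up for survival and for response from standard-of-care assessments. Align the OS population in the synopsis with objective 2.2.6.
2. **Section 8.1.** Keep 12 of 37 dosed patients as the activity test, and state that its 5% error applies to that population.
3. **Section 8.3.** Pre-specify a CR/CRi rate with exact 95% confidence interval in all patients who start cytarabine, counting undosed patients as non-CR. Add a sensitivity analysis using their observed response, noting any later anti-leukaemic therapy. Report the numbers undosed and replaced, and read the comparison with 20% alongside this rate.

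The all-starter rate should be descriptive, not a second pass/fail test. Even with nobody undosed, the interval for 12/37 starts at 18.0% and the single-stage tail probability P(X ≥ 12 | 37, 0.20) is 0.0517, so either criterion would overturn a valid two-stage rejection. Making 37 starters the test denominator would also cost power: with a dosed-patient rate of 40% and undosed patients as failures, it falls to 0.79, 0.71, 0.62 and 0.52 at 5, 10, 15 and 20% undosed.

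The cost is protocol and SAP wording plus follow-up of patients already enrolled, which may be incomplete for any already removed. Sample size, cut-off and power do not change. The drawback is a less favourable headline rate: counting undosed patients as non-CR is conservative, hence the sensitivity analysis.
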